11.2. WHO Stage 4 conditions (WHO 2006 revision)

- HIV wasting syndrome
- pneumocystis pneumonia
- recurrent severe bacterial pneumonia
- chronic herpes simplex infection (orolabial, genital or anorectal of more than 1 month's duration or visceral at any site)
- oesophageal candidiasis (or candidiasis of trachea, bronchi or lungs)
- extrapulmonary TB
- Kaposi's sarcoma
- cytomegalovirus infection (retinitis or infection of other organs)

- central nervous system toxoplasmosis
- HIV encephalopathy
- extrapulmonary cryptococcosis including meningitis
- disseminated non-tuberculous mycobacteria infection
- progressive multifocal leukoencephalopathy
- chronic cryptosporidiosis
- chronic isosporiasis
- disseminated mycosis (extrapulmonary histoplasmosis, coccidiomycosis)
- recurrent septicaemia (including non-typhoidal salmonella)
- lymphoma (cerebral or B cell non-Hodgkin)
- invasive cervical carcinoma
- atypical disseminated leishmaniasis
- symptomatic HIV-associated nephropathy
- symptomatic HIV-associated cardiomyopathy.

11.3. Drug-induced liver injury (DILI)

DILI will be defined using the ACTG grading system (see section 22.2: DIVISION OF AIDS TABLE FOR GRADING THE SEVERITY OF ADULT AND PEDIATRIC ADVERSE EVENTS VERSION 1.0, DECEMBER, 2004; CLARIFICATION AUGUST 2009). We will specifically classify Grade 2, 3 or 4 elevations of ALT and total bilirubin as DILI: ALT elevation 2.6-5 x upper limit of normal is grade 2, 5.1-10 x upper limit of normal is grade 3 and > 10 x upper limit of normal is grade 4. Total bilirubin elevation 1.6-2.5 x upper limit of normal is grade 2, 2.6-5 x upper limit of normal is grade 3 and > 5 x upper limit of normal is grade 4.

We will further differentiate clinical hepatitis (these elevations together with symptoms of hepatitis: nausea, vomiting, right upper quadrant pain or lethargy) from all biochemical hepatitis (any elevation above these levels regardless of whether symptomatic or asymptomatic).

11.4. Drug rash

A drug rash will be defined as any rash the onset of which is after the initiation of a drug or drugs, the morphology and natural history of which is compatible with a drug rash. Cases in which the aetiology is unclear will be reviewed by a Dermatologist (either seeing the patient or digital photographs taken of the rash).

11.5. Corticosteroid-associated adverse events

Clinical symptoms and signs that could possibly be attributed to corticosteroids side effects will be documented and recorded as corticosteroid-associated adverse events. This will include: new hypertension (resting BP: systolic > 160 mmHg or diastolic >100mmHg), new poor BP control in known hypertensive (who reports adherence to anti-hypertensive therapy, using same thresholds for systolic and diastolic BP), hyperglycaemia (random glucose > 11.1 mmol/l), new oedema, hypomania/mania (diagnosed by psychiatrist), depression (diagnosed by psychiatrist), Cushingoid features or habitus (in the opinion of the clinical investigator),

acne, gastritis symptoms (epigastric pain), upper gastro-intestinal bleeding or avascular bone necrosis. Avascular necrosis will be investigated if patients present with symptoms of bone pain.

Only features that develop while patients are on the study drug or for the 4 weeks afterwards will be classified as corticosteroid side effects.

Infections will not be recorded under corticosteroid side effects but will be recorded and analysed separately.

12. Laboratory evaluation

All laboratory tests (blood and sputum) will be performed at the National Health Laboratory Services laboratories at Green Point or Groote Schuur Hospital. These laboratories are SANAS (South African National Accreditation System) accredited and experienced in performing investigations for clinical research. Hard copy reports of all results will be forwarded to the clinical trial team as soon as the investigation result is available. These will be signed and dated by the trial team. If there is an abnormality then appropriate action will be taken (eg. recalling patient) and this will be documented on the hard copy result. All abnormal investigation results will be communicated to the TB and ART clinic staff.

13. Clinical Management

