The above findings mainly apply to HIV-negative patients and there are concerns regarding the use of adjuvant corticosteroids in HIV-infected patients. In a Ugandan trial that evaluated prednisolone in HIV-infected patients with TB pleural effusions, prednisolone was associated with more rapid clinical and radiological improvement, but an excess of Kaposi's sarcoma [26]. A study was conducted in Uganda specifically in HIV-infected patients with pulmonary TB, but prior to ART availability. In this phase 2 trial of short-term prednisolone in HIV-infected TB patients with CD4 count ≥ 200 cells/mm³, prednisolone was associated with more rapid clearance of MTB from sputum, reduced immune activation and resulted in a non-significant increase in CD4 count, but caused a transient increase in HIV viral load and worsened underlying hypertension and caused fluid retention and hyperglycaemia. High dose prednisolone was used in this trial (initially 2.75mg/kg/day for 4 weeks) [27]. Other corticosteroid trials in HIV-infected patients have raised concerns related to reactivation of herpes infections [28]. All patients on our proposed trial will be on ART, and ART is likely to be at least partially protective against certain of these corticosteroid side effects, such as the development of Kaposi's sarcoma.

Corticosteroids have drug-drug interactions with rifampicin, a potent inducer of cytochrome P450 enzymes. Rifampicin increases the clearance of prednisolone by 45% resulting in reduction in the area under the plasma concentration time curve of prednisolone by 66% [29].

We factored this in our decision regarding prednisone dose for this trial.

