14.1. Sample size calculation

Assuming 35% cumulative incidence of TB-IRIS in the placebo arm and a 50% reduction in TB-IRIS in the corticosteroid arm (ie. to 17.5%) and requiring 80% power to test for the difference in TB-IRIS incidence at a two-sided significance level of 5%, the sample size required would be 110 in each arm. We will aim to recruit 240 patients assuming loss to follow-up of 10%. The estimate of 35% incidence of TB-IRIS in the placebo arm corresponds to the findings of Blanc et al (110/332 (33%) of participants who started ART in the early arm in this trial had TB-IRIS events (32)) and a study we conducted at Brooklyn Chest TB Hospital in Cape Town (42% IRIS incidence [47]) and reflects that these will be patients at high risk for TB-IRIS due to low CD4 counts and short interval between TB treatment and ART start. Lawn and colleagues demonstrated in a retrospective study conducted in Cape Town that low CD4 count and shorter interval between TB treatment and ART initiation were the strongest predictors of TB-IRIS. In their study 70% of patients with a CD4 count < 100/μl who started ART within 30 days of TB treatment developed TB-IRIS [48].

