- p) Comparison of quality of life assessment between the two arms at week 4 and at week 12. In the trial, the following measurements were performed: PROQOL-HIV, EQ-5D-3L, HIV symptom index and Karnofsky score. For EQ-5D-EL we will compare the proportion of patients in the different domain levels using the Chi-square test, and we will compare the means of the VAS score using the t-test or Wilcoxon rank sum test as appropriate. For the adapted ProQOL HIV the summary score per domain (adapted from [1]) will be compared using the t-test

or Wilcoxon rank sum test as appropriate. For the HIV-symptom index the frequency (proportion) and the severity of each symptom (score 1-2 vs score 3-4) will be compared using the Chi-square test. Because of multiplicity, Bonferroni correction will be applied in the analysis of HIV symptoms. Karnofsky score will be compared using the t-test or Wilcoxon rank sum test as appropriate.

- q) The cumulative proportion of participants who develop adverse events ascribed to TB treatment, ART or co-trimoxazole requiring interruption of one or more of these medications (for > 5 days) within 12 weeks of randomisation will be compared using Chi-square test or Fisher exact test (as appropriate).
- r) The cumulative proportion of participants who develop drug rash or drug-induced liver injury ascribed to TB treatment, ART or co-trimoxazole and requiring interruption of one or more of these medications (for > 5 days) within 12 weeks of randomisation will be compared using Chi-square test or Fisher exact test (as appropriate).

5. Analysis of secondary safety and tolerability endpoints

A number of secondary safety and tolerability analyses will be performed, all using the all-patients-treated approach (this excludes those participants who were randomized but never started study medication and/or ART).

- a) Comparison of proportion of participants in each arm who develop at least one of the pre-specified potential corticosteroid-associated adverse events within 4 weeks and within 12 weeks of randomization using Chi-square test or Fisher exact test (as appropriate). The proportion of participants in each group who develop individual potential corticosteroid-associated adverse events within 4 weeks and within 12 weeks of randomization will also be compared.

The pre-specified potential corticosteroid-associated adverse events are:

- New hypertension > 160/100
- New poor BP control on treatment > 160/100

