- Hyperglycaemia (random glucose > 11.1 mmol/l)

- Hypomania/mania
- Depression
- Acne
- Epigastric pain
- Upper gastro- intestinal bleeding
- Cushingoid features
- New oedema
- Avascular bone necrosis

b) Comparison of laboratory safety bloods done at week 2, 4 and 12: sodium, potassium, creatinine, ALT, alkaline phosphatase, total bilirubin, glucose, haemoglobin, white cell count, neutrophil count, total lymphocyte count and platelets. Comparison of medians will be performed at each time point using the Wilcoxon rank sum test. The proportion of participants who develop an ACTG grade 3 or grade 4 abnormality in these blood tests will also be compared using Chi-square test or Fisher exact test (as appropriate).

c) Comparison of week 12 CD4 count and HIV viral load results. Comparison of medians will be performed using the Wilcoxon rank sum test. Proportion of participants with less than $2 \log_{10}$ drop in HIV viral load from screening to week 12 will be compared using the Chi-square test or Fisher exact test (as appropriate). Where screening viral load was too low to ascertain a $2 \log_{10}$ drop then an undetectable viral load at week 12 will be regarded as successful outcome.

d) Comparison of the proportion of participants who are diagnosed with other infections (AIDS-related, bacterial, fungal and viral) and malignancies (Kaposi's sarcoma) will be compared using Chi-square test or Fisher exact test (as appropriate). These will also be presented with individual listing. The proportion with severe infections (classified as any AIDS-defining (WHO stage 4) infection or invasive bacterial infection) will be compared in a separate analysis.

e) The proportion of participants with any clinical ACTG grade 1, 2, 3 and 4 adverse events (AEs) will be compared using Chi-square test or Fisher exact test (as appropriate). A similar comparison will be made for serious adverse events (SAEs) and adverse drug reactions (ADRs) attributed as definite, probably or possibly due to medication (the relationship between ADRs and medication has been determined by the study doctors and categorized as definitely not, unlikely, possibly, probably or definitely related to any medication).

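### Blood pressure as a steroid harm is tested only as a crossing of 160 or 100 mmHg, never as a measurement, which leaves little power to detect a modest rise

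*Supplement*

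**What the plan says.** Protocol v1.4 section 11.5 lists the corticosteroid-associated adverse events. The first is "new hypertension (resting BP: systolic > 160 mmHg or diastolic >100mmHg"; the second is new poor control in a known hypertensive, at the same limits. SAP section 5(a) carries these over as two items, the first written as "New hypertension > 160/100". It compares the proportions with a chi-square or Fisher test within 4 and within 12 weeks, for each item and for any item combined.

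SAP section 5(b) is headed "Comparison of laboratory safety bloods done at week 2, 4 and 12" and names twelve laboratory variables. Each is compared as a median at each time point and as a proportion with a grade 3 or 4 abnormality. Glucose is one of the twelve, and hyperglycaemia is also an event in 5(a). Blood pressure is not in 5(b) or in any other comparison of measured values.

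Two other routes exist. All grade 1-4 clinical adverse events are recorded (protocol section 18.1) and compared between arms (SAP 5(e)), and events are listed by MedDRA preferred term and body system.

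**The concern.** Hypertension is a named steroid harm, and protocol section 3.3 cites a trial in HIV-associated TB in which prednisolone "worsened underlying hypertension and caused fluid retention and hyperglycaemia". The primary objective (section 3.1) pairs efficacy with the absence of extra harm. Reducing a continuous measurement to a high cut loses most of its information when few participants are near the cut. If events are sparse, a non-significant result says little about how large a rise the trial can exclude. A mean difference with its confidence interval would say exactly that. The SAP already does this kind of analysis for laboratory values, but not for blood pressure.

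**Working it through.** **The plan's own figure.** Section 14.1 says "the sample size required would be 110 in each arm". For 35% against 17.5%, two-sided 5% and 80% power, the two-proportion formula gives 99 per arm, and 110 with continuity correction. The figure reproduces, but it sizes TB-IRIS only. The documents give no blood pressure mean, SD, event rate or expected shift, so everything below on power rests on assumptions. The 240 enrolled give 120 per arm.

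**A bound that needs no blood pressure assumption.** With no placebo events and 5 prednisone events among 120 per arm, two-sided Fisher p = 2 × (120·119·118·117·116)/(240·239·238·237·236) = 0.060. A sixth event multiplies this by 115/235, giving p = 0.029. At least six events against none are needed for p < 0.05.

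**Event comparison.** Simulated: any of five follow-up visits with systolic > 160 or diastolic > 100; normal readings; between-visit correlation 0.6; systolic-diastolic correlation 0.6; shift at the first three visits only (weeks 1, 2 and 4); diastolic shift 0.6 of the systolic shift. Exact Fisher power, two-sided 5%, 120 per arm:

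| Placebo mean, mmHg (SD) | +3 | +5 | +8 | +10 |
|---|---|---|---|---|
| 115/72 (15/10) | 1.0% | 2.6% | 11% | 24% |
| 115/72 (18/12) | 3.9% | 7.4% | 23% | 41% |
| 120/76 (15/10) | 3.8% | 8.6% | 29% | 52% |
| 120/76 (18/12) | 5.7% | 13% | 35% | 57% |
| 125/80 (15/10) | 6.5% | 16% | 51% | 76% |
| 125/80 (18/12) | 7.3% | 17% | 47% | 71% |

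Event rates at +5 mmHg run from 1.5% vs 2.8% (first row) to 19% vs 25% (last row).

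**Comparison of systolic means, one visit, unadjusted.** Power = Φ(δ/(SD·√(2/n)) − 1.96).

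- SD 15, δ = 5, n = 120: 5/(15 × 0.1291) = 2.582, and Φ(0.622) = 73%.
- SD 18, δ = 3: 3/2.324 = 1.291, and Φ(−0.669) = 25%.
- SD 18, δ = 8: 8/2.324 = 3.443, and Φ(1.483) = 93%.
- SD 15, δ = 10: above 99%.

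For SD 15-18 the range is therefore 25-73% at 3-5 mmHg and 93% or more at 8-10 mmHg. An SD of 12 would raise the upper figure at 5 mmHg to 90%.

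**Gain from adjusting for week 0.** Replace SD by SD·√(1 − r²). With 115 per arm, SD 15 and δ = 5, power is 71% unadjusted, 79% at r = 0.4 and 88% at r = 0.6.

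**Limits of the check.** The simulation does not remove people already above the cut at week 0, so its event rates are on the high side. It covers the 12-week comparison, not the 4-week one. It uses Fisher throughout, whereas the SAP allows chi-square when counts permit, which is somewhat less conservative.

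**The case against.** The strongest case against has several parts.

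- **Lower rises are not ignored.** A rise below the limits that is recorded as an adverse event enters the grade 1-4 comparison and appears under its own MedDRA term. This stands: a reader might infer that the whole plan counts blood pressure harm only above 160/100, and the documents do not support that. But the 5(e) comparison pools all clinical adverse events and the MedDRA output is a listing, so no planned test isolates blood pressure. The grading table's cut-offs are not in the supplied text and cannot be checked.
- **Loss of power depends on the shift.** A reader might infer that any real rise would almost certainly be missed. That does not hold: at 8-10 mmHg the event comparison reaches 51-76% in its best scenarios.
- **The cited precedent is weak.** It used high-dose prednisolone and concerned underlying hypertension, which the separate poor-control item covers. The investigators' earlier trial, at higher doses than this one, found no excess of metabolic side effects. Both are fair and temper the prior expectation of harm.
- **Marked hypertension is a legitimate event, and glucose is in 5(b) because it is a laboratory test.** True; the event should stay. This explains where glucose sits, but gives no reason to leave blood pressure unmeasured in the analysis.
- **The SAP's shorthand.** It can be read as requiring both values, but the SAP defers to the protocol, whose section 11.5 says either. This is a minor wording repair, not a contradiction.
- **Data and multiplicity.** The schedule has no blood pressure or vital-signs row, so recording is inferred. Testing two pressures at five visits would add ten comparisons. Both points shape the remedy.

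**Conclusion.** The point holds as a gap in the safety analysis. Within the corticosteroid-associated endpoint, blood pressure is tested only as a yes/no crossing, and nothing in the SAP compares it as a measurement. Under the stated assumptions the event comparison is weak for a modest rise and of mixed strength for a larger one, while a comparison of means has more power in every scenario computed. The ranges move with the assumed means, SDs and correlations. The direction was the same throughout, and the case for an interval estimate does not depend on any single scenario. The documents do not show that harm would be read as absent, and they do not make the existing event wrong. This is a worthwhile supplement, not a flaw in the primary analysis.

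**What to change.** In SAP section 5(a), keep both events and write the limit with the protocol's either-value wording. Add a supplementary safety analysis of systolic and diastolic pressure at weeks 1, 2 and 4, for example one repeated-measures model per pressure adjusted for the week 0 value, reporting the mean difference between arms with its 95% CI. Show weeks 8 and 12 descriptively only, because the SAP itself notes that open-label corticosteroids blur the later contrast. They generally start from 2-3 weeks, so week 4 is already partly affected, though the SAP accepts the first four weeks as the cleaner window.

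The cost is a short SAP addition before unblinding, with no new visits. The section 11.5 event already requires resting pressure; the sponsor should confirm that it was recorded at each physical examination. If it was not, the existing event is incompletely ascertained too, and the report should say so. The downside is two extra safety comparisons, to be read by their intervals rather than as tests.

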13.1. Co-trimoxazole prophylaxis

All patients on the clinical trial are eligible for co-trimoxazole primary prophylaxis, unless they are known to have a sulphonamide allergy. This is because all eligible study patients are HIV-infected with CD4 < 100 cells/ μ l and have WHO stage 3 or 4 disease. The co-trimoxazole dose used for primary prophylaxis will be 960mg daily (2 tablets). In those patients who cannot take co-trimoxazole or who develop an allergic reaction while on co-trimoxazole then dapsone 100mg daily will be considered as an alternative. In cases where patients have had life-threatening co-trimoxazole reactions (eg. Stevens Johnson syndrome) then dapsone will not be used as there a small risk of cross-reactivity.

13.2. Management of suspected TB-IRIS

In patients who deteriorate with clinical or radiographic features of TB after starting ART paradoxical TB-IRIS will be a consideration. This will include patients who develop new or recurrent TB symptoms or fever, enlarging lymph nodes or worsening chest radiograph pulmonary infiltrates, enlarging effusions or TB neurological features. At any such deterioration suggestive of paradoxical TB-IRIS (at a scheduled or unscheduled sick visit) the following investigations will be performed:

- 1) Bacterial blood culture
- 2) Creatinine/electrolytes/glucose, liver functions, full blood count/differential, CRP, serum CrAg (cryptococcal antigen test)
- 3) Sputum and other biological samples for MTB/RIF Xpert, culture and DST

- 5) Chest radiograph
- 6) Other investigations according to clinical presentation (eg. abdominal ultrasound, lumbar puncture, CT head)

The principal aim of these investigations is to exclude alternative causes for clinical deterioration as the diagnosis of paradoxical TB-IRIS is a diagnosis of exclusion. In addition, the adherence of patients to ART and TB medication will be checked by means of an interview with the patient and treatment buddy, and counting pills in the pill container and checking with the TB clinic staff.

If paradoxical TB-IRIS is diagnosed (fulfilling INSHI case definition for paradoxical TB-IRIS), open label corticosteroids will be prescribed for IRIS treatment at physician discretion. Study drug will be stopped on the day the decision is made to start open label corticosteroids. The decision to commence corticosteroids to treat TB-IRIS and exact timing is an individualized one that is based on physician discretion and takes into account the severity of symptoms and the confidence with which alternative causes for clinical deterioration have been excluded.

The prednisone starting dose to treat TB-IRIS will be 1.5mg/kg/day and this will be reduced according to clinical response. In patients with central nervous system TB-IRIS the initial corticosteroid used may be dexamethasone intravenously.

13.3. Management of new opportunistic infections or malignancies

If patients are diagnosed with a new opportunistic infection or malignancy while on the trial they will be referred to the appropriate level of care and management will be according to national Department of Health guidelines for the treatment of opportunistic infections. For example, patients with cryptococcal meningitis will be treated with amphotericin B followed by fluconazole.

When a new WHO stage 4 opportunistic infection or malignancy is diagnosed while patients are on study medication this will be an indication for stopping study medication. For certain opportunistic infections it may be indicated to start corticosteroid therapy (eg. pneumocystis pneumonia with respiratory failure). This decision will be taken by the attending clinician and open label corticosteroid therapy will be documented.

13.4. Management of drug reactions

If TB drug-induced liver injury occurs during follow-up cases will be managed according to the local clinical guidelines (Western Cape Academic Hospitals Antimicrobial Recommendations). These guidelines are based on the American Thoracic Society guidelines for management of TB drug hepatotoxicity [46]:

Hepatotoxicity

TB drug-induced hepatitis is over-diagnosed: the case definition is transaminases more than 5-fold elevated or more than 3-fold elevated with symptoms/jaundice. Antituberculous therapy should be discontinued. The basis for the TB diagnosis should be reviewed. If the grounds for diagnosing TB were reasonable then commence three antituberculous drugs with low/no hepatotoxic potential (see background therapy below). Selected patients may then be rechallenged once symptoms of hepatitis have resolved, bilirubin levels return to normal and transaminases have decreased to <100. Rechallenge is **NOT** recommended for those who have had fulminant hepatitis (defined as hepatic encephalopathy with coagulopathy).

The rechallenge regimen of the American Thoracic Society (Am J Respir Crit Care Med 2006;174:935–52) have been followed as these are simple and quick. Rechallenge with PZA was previously not recommended, but a recent trial has shown that most patients tolerate it. PZA rechallenge should be considered in patients with severe TB (e.g. miliary, meningitis) or with drug resistance. Transaminase levels, especially ALT, should be monitored frequently (e.g. three times weekly) during rechallenge and every two weeks for a month following rechallenge.

If possible all patients with a drug induced liver injury should have their TB isolates sent for drug susceptibility testing. Do not rechallenge with an agent to which the isolate is resistant.

| | | |
|----------------------|--------------------|--|
| rechallenge regimen: | Background therapy | Ethambutol, streptomycin and moxifloxacin. |
| | day 1 | Rifampicin 450 or 600 mg daily depending on weight |
| | day 3 | Check ALT |
| | day 4 | Add INH 300mg daily |
| | day 7 | Check ALT |
| | day 8 | Consider PZA rechallenge (see text) |

NB: Duration of therapy should be individualised after rechallenge – consult ID for advice. The following are guidelines:

- Pyrazinamide not rechallenged/not tolerated: stop moxifloxacin and streptomycin, continue isoniazid, rifampicin and ethambutol for total duration 9 months
- Rifampicin not tolerated: continue streptomycin (for 2 months) and moxifloxacin, isoniazid, and ethambutol for total duration of 18 months
- Isoniazid not tolerated: stop moxifloxacin and streptomycin, add ethionamide (if tolerated – otherwise use moxifloxacin) to rifampicin and ethambutol for total duration 12 months

In addition, if significant liver impairment occurs or patients have symptoms of hepatitis with

liver function derangements then adjustments will be made to the ART regimen (omitting efavirenz and considering replacing it with an alternative ART agent, or stopping all ART if acute liver failure develops). In there is significant DILI co-trimoxazole and other potential hepatotoxic medication will also be stopped. Rechallenge of ART and other potential hepatotoxins will be considered and rechallenge will generally be done after rechallenge of TB medication. Management of each case will be individualized and discussed with the PI.

If patients develop drug rash on the trial this could be potentially related to co-trimoxazole (a frequent cause of drug rashes), efavirenz or one of the TB drugs. For very mild rashes they will be monitored with regular review and symptomatic therapy. In patients with more significant symptoms at presentation or who develop more severe clinical features (extensive rash, fever, systemic symptoms, blistering or desquamation, angio-oedema or mucosal involvement) all potential culprit drugs will be stopped immediately. Patients will be managed in consultation with the Groote Schuur Hospital Division of Dermatology either by sending digital photographs for an opinion or by referral of the patients for outpatient or inpatient management. Rechallenge of drugs after a drug rash will follow local guidelines.

[figure not shown]
The Groote Schuur Hospital guidelines for the management of cutaneous drug reactions (CDRs) while on TB treatment will be followed:

Mild rash in isolation without systemic symptoms, mucosal involvement or abnormal LFTs can be treated with oral antihistamines and skin moisturizing agents, whilst continuing the drug under close observation.

Severe rashes involve mucosal membranes and are associated with systemic syndromes
Stevens-Johnson Syndrome - <10% skin detachment
Toxic Epidermal Necrolysis - >30% skin detachment
DRESS syndrome – Drug rash eosinophilia and systemic symptoms

The following algorithm will be used for management of severe CDR. If ART also needs to be stopped, then re-start after TB drug rechallenge is complete and consider a PI-based regimen should the patient have previously been on an NNRTI.

Management of severe CDR:

